5.2. Exclusion Criteria

Participants are excluded from the study if any of the following criteria apply:

1. Prior receipt of an FGFR inhibitor.
2. Receipt of anticancer medications or investigational drugs for any indication or reason within 28 days before first dose of study drug. Participants must have recovered (\leq Grade 1 as per CTCAE v5.0 or at pretreatment baseline) from AEs from previously administered therapies (excluding alopecia).
3. Participants may have had treatment for an unlimited number of prior relapses but must not have had prior bevacizumab or other VEGF/VEGFR inhibitors (exception: prior bevacizumab is allowed if it was administered for the treatment of radiation necrosis rather than progressive tumor and was stopped at least 12 weeks prior to MRI showing tumor progression).
4. Concurrent anticancer therapy (eg, chemotherapy, immunotherapy, biologic therapy, hormonal therapy, investigational therapy, or tumor embolization).
5. Candidate for potentially curative surgery.
6. Dexamethasone (or equivalent) > 4 mg daily at the time of study registration (higher dose of steroid for symptom control is allowed during the study).
7. Current evidence of clinically significant corneal (including but not limited to bullous/band keratopathy, corneal abrasion, inflammation/ulceration, and keratoconjunctivitis) or retinal disorder (including but not limited to macular/retinal degeneration, diabetic retinopathy, and retinal detachment) as confirmed by ophthalmologic examination.
8. Diffuse leptomeningeal disease.
9. Radiation therapy administered within 12 weeks before enrollment/first dose of study drug. An interval of at least 12 weeks after prior radiotherapy is required unless there is either histopathological confirmation of recurrent tumor or new enhancement on MRI outside the radiotherapy field.
10. Known additional malignancy that is progressing or requires active systemic treatment. Exceptions include basal cell carcinoma of the skin, squamous cell carcinoma of the skin, or *in situ* cervical cancer that has undergone potentially curative therapy.
11. Participants with laboratory values at screening defined in [Table 7](#).

Table 7: Exclusionary Laboratory Values

| Laboratory Parameter | | Exclusion Criterion |
|-----------------------------|----------------------------|--|
| Hematology | | |
| a | Platelets | $\leq 75 \times 10^9/\text{L}$ (transfusion allowed with a 2-week washout period) |
| b | Hemoglobin | $\leq 9 \text{ g/dL}$ (transfusion allowed with a 2-week washout period) |
| c | ANC | $\leq 1.5 \times 10^9/\text{L}$ |
| Hepatic | | |
| d | ALT | $\geq 3 \times \text{ULN}$ ($> 5 \times \text{ULN}$ for liver metastasis) |
| e | AST | $\geq 3 \times \text{ULN}$ ($> 5 \times \text{ULN}$ for liver metastasis) |
| f | Total bilirubin | $\geq 1.5 \times \text{ULN}$ ($\geq 2.5 \times \text{ULN}$ if Gilbert's syndrome or liver metastasis) |
| g | Alkaline phosphatase | $\geq 3 \times \text{ULN}$ |
| Renal | | |
| h | Serum creatinine clearance | $\leq 30 \text{ mL/minute}$ based on Cockcroft-Gault formula |
| Chemistry | | |
| i | Serum phosphate | $> \text{ULN}$ |
| j | Serum calcium | Outside of normal range or serum albumin-corrected calcium outside of the normal range when serum albumin is outside of the normal range |

12. History of calcium and phosphate homeostasis disorder or systemic mineral imbalance with ectopic calcification of soft tissues (exception: commonly observed calcifications in soft tissues such as the skin, kidney tendon, or vessels due to injury, disease, or aging in the absence of systemic mineral imbalance).
13. Significant gastrointestinal disorder(s) that could interfere with absorption, metabolism, or excretion of study drug.
14. Clinically significant or uncontrolled cardiac disease including unstable angina, acute myocardial infarction within 6 months before Day 1 of study drug administration, New York Heart Association Class III or IV congestive heart failure, and uncontrolled arrhythmia (participants with pacemaker or with atrial fibrillation and well controlled heart rate are allowed).
15. History or presence of an abnormal ECG that, in the investigator's opinion, is clinically meaningful. A screening QTcF interval > 480 milliseconds is excluded. For participants with an intraventricular conduction delay (QRS interval > 120 ms), the JTc interval may be used in place of the QTc with medical monitor approval. The JTc must be ≤ 340 milliseconds if JTc is used in place of the QTc.
16. Active chronic or current infectious disease requiring systemic antibiotic, antifungal, or antiviral treatment within 2 weeks before enrollment (participants with asymptomatic chronic infections on prophylactic treatment are allowed).

17. Evidence of active HBV or HCV infection (defined as participants with elevated transaminases or cirrhosis). Participants with chronic HBV/HCV infection with no cirrhosis and no elevated transaminases are allowed.
18. Participants with a known HIV infection who have CD4⁺ T-cell count < 350 cells/ μ L will be excluded. Participants with CD4⁺ T-cell (CD4⁺) counts \geq 350 cells/ μ L should generally be eligible.
19. Current use of prohibited medication as described in Section 6.6.2.
20. Use of any potent CYP3A4 inhibitors or inducers or moderate CYP3A4 inducers (see [Appendix D](#)) within 14 days or 5 half-lives (whichever is longer) before the first dose of study drug. Moderate CYP3A4 inhibitors are not prohibited but should be avoided (see Section 6.6.1).
21. Known hypersensitivity or severe reaction to pemigatinib or excipients of pemigatinib ([Pemazyre 2021a](#), [Pemazyre 2021b](#)).
22. Inability or unlikelihood of the participant to comply with the dose schedule and study evaluations, in the opinion of the investigator.
23. Inadequate recovery from toxicity and/or complications from a major surgery before starting therapy.
24. Women who are pregnant or breastfeeding. For Japan, women who are breastfeeding and wish to enroll must discontinue breastfeeding at least 90 days before receiving study drug. They must also refrain from breastfeeding during the course of study and for 90 days after the last dose of study drug.
25. Any condition that would, in the investigator's judgment, interfere with full participation in the study, including administration of study drug and attending required study visits; pose a significant risk to the participant; or interfere with interpretation of study data.
26. History of hypovitaminosis D requiring supraphysiologic doses (eg, 50,000 UI/weekly) to replenish the deficiency. Vitamin D supplements are allowed.
27. The following participants are excluded in France: vulnerable populations according to article L.1121-6 of the French Public Health Code and adults under legal protection or who are unable to express their consent per article L.1121-8 of the French Public Health Code.

5.3. Lifestyle Considerations

Based on the preliminary results from the food effect cohort in Study INCB 54828-101, no significant food effect was observed. Pemigatinib may be administered with or without food.

Participants should refrain from consumption of red wine, Seville oranges, grapefruit or grapefruit juice, pomelos, exotic citrus fruits, grapefruit hybrids, or fruit juices that contain potent CYP3A4 inhibitors from 14 days before the start of study treatment until after the final dose, as this can affect the metabolism of the study drug.

5.4. Screen Failures

Screen failures are defined as participants who consent to participate in the clinical study but are not subsequently entered in the study.

Individuals who do not meet the criteria for participation in this study (screen failure) may be rescreened no more than 1 time.

Tests with results that fail eligibility requirements may be repeated once during screening if the investigator believes the result to be in error. Additionally, a participant who fails screening may repeat the screening process 1 time if the investigator believes that there has been a change in eligibility status. Participants who rescreen must reconsent and be assigned a new participant number.

5.5. Replacement of Participants

No participants will be replaced at any time during this study.

6. STUDY TREATMENT

6.1. Study Treatment Administered

Table 8 presents the study treatment information. The starting dose of pemigatinib for all participants is 13.5 mg QD.

Table 8: Study Treatment Information

| | |
|--|---|
| Study treatment name: | Pemigatinib/INCB054828 |
| Mechanism of action: | Targeted inhibitor of FGFR1-3 |
| Dosage formulation: | Tablet |
| Unit dose strength(s)/dosage level(s): | 13.5 mg, 9 mg, and 4.5 mg |
| Route of administration: | Oral |
| Administration instructions: | One tablet taken every morning (unless otherwise directed) for 2 weeks and then 1 week off |
| Packaging and labeling: | Pemigatinib will be provided in bottles; each bottle will be labeled as required per country requirement. |
| Storage: | Room temperature (15°C-30°C) |
| Status of treatment in participating countries: | Investigational |

6.2. Preparation, Handling, and Accountability

The investigator or designee, or investigational drug storage manager (for Japan), must confirm appropriate temperature conditions have been maintained during transit for all study treatments received and any discrepancies are reported and resolved before use of the study treatment.

Only participants enrolled in the study may receive study treatment, and only authorized site staff may supply or administer study treatment. All study treatments must be stored in a secure, environmentally controlled, and monitored (manual or automated) area in accordance with the labeled storage conditions with access limited to the investigator, investigational drug storage manager (for Japan), and authorized site staff.

The investigator, investigational drug storage manager (for Japan), or designee is responsible for study treatment accountability, reconciliation, and record maintenance (ie, receipt, reconciliation, and final disposition records). Inventory and accountability records must be maintained and readily available for inspection by the study monitor and are open to inspection at any time by any applicable regulatory authorities. The investigator, investigational drug storage manager (for Japan) or designee must maintain records that document the following:

- Delivery of study drug to the study site.
- Inventory of study drug at the site.
- Participant use of the study drug, including pill counts from each supply dispensed.
- Return of study drug to the investigator, investigational drug storage manager (for Japan), or designee by participants.

The investigational product must be used only in accordance with the Protocol (see [Appendix C](#)). The investigator will also maintain records adequately documenting that the participants were provided the specified study drug. These records should include dates, quantities, and any available batch or serial numbers or unique code numbers assigned to the investigational product and study participants.

Completed accountability records will be archived by the site. The investigator, investigational drug storage manager (for Japan), or designee will be expected to collect and retain all used, unused, and partially used containers of study drug until verified by the study monitor (unless otherwise agreed to by the sponsor). At the conclusion of the study, the investigator, investigational drug storage manager (for Japan), or designee will oversee shipment of any remaining study drug back to the sponsor or its designee for destruction according to institutional SOPs. If local procedures mandate on-site destruction of the investigational supply, the site should (where local procedures allow) maintain the investigational supply until the study monitor inspects the accountability records in order to evaluate compliance and accuracy of accountability by the investigative site. At sites where the study drug is destroyed before monitor inspection, the monitors rely on documentation of destruction per the site SOP.

Further guidance and information for the final disposition of unused study treatments are provided in the Pharmacy Manual.

6.3. Measures to Minimize Bias: Randomization and Blinding

This is an open-label, nonrandomized study.

6.4. Study Treatment Compliance

Compliance with all study-related treatments should be emphasized to the participant by the site personnel, and appropriate steps should be taken to optimize compliance during the study. Compliance with pemigatinib will be calculated by the sponsor based on the drug accountability (ie, tablet counts) documented by the site staff and monitored by the sponsor/designee. Participants will be instructed to bring all unused study drug with them to the study visits in order for site personnel to conduct tablet counts to assess study drug accountability.

6.5. Dose Modifications

Individual decision regarding dose modifications of pemigatinib should be made using clinical judgment and in consultation with the sponsor's medical monitor, taking into account relatedness of the AE to the study drug and the participant's underlying condition. Adverse events that have a clear alternative explanation or transient (≤ 72 hours) abnormal laboratory values without associated clinically significant signs or symptoms may be exempt from dose reduction rules.

6.5.1. Criteria and Procedures for Dose Interruptions and Adjustments of Study Drug

Safety concerns should be discussed with the sponsor immediately upon occurrence or awareness to determine if the participant should continue or discontinue study treatment.

Adverse events associated with pemigatinib can often be managed with concomitant medications, supportive care, and/or dose modifications as per [Table 9](#). Each treatment intervention should be clearly documented in the eCRF.

Treatment with pemigatinib may be delayed up to 2 weeks (14 days) to allow for resolution of toxicity. Participants may resume treatment if no medical condition or other circumstance exists that, in the opinion of the investigator, would make the participant unsuitable for further participation in the study. The treating investigator should contact the sponsor to discuss the case of any participant whose treatment has been delayed for more than 14 days before restarting treatment with pemigatinib.

Table 9: Guidelines for Interruption and Restarting of Study Drug

| Adverse Event | Action Taken |
|--|---|
| Chemistry | |
| • AST and/or ALT is $> 5.0 \times \text{ULN}$. | Step 1: Interrupt study drug up to 2 weeks (14 days) until the toxicity has resolved to \leq Grade 1 or baseline except by approval of the medical monitor. Step 2: Restart study drug at same dose. If assessed as related to study drug, restart study drug at next lower dose; monitor as clinically indicated. |
| Other toxicities | |
| • Any Grade 1 or Grade 2 toxicity. | Continue study drug treatment and treat the toxicity; monitor as clinically indicated. |
| • Any Grade 3 toxicity | Step 1: Interrupt study drug up to 2 weeks (14 days) until toxicity resolves to \leq Grade 1 or baseline. Step 2: Restart study drug at same dose. If assessed as related to study drug, restart study drug at next lower dose; monitor as clinically indicated. |
| • Any recurrent Grade 3 toxicity after 2 dose reductions. | Discontinue study drug administration and follow-up per Protocol. (Exceptions require approval of sponsor.) |
| • Any other Grade 4 toxicity. • QT/QTc to $> 500 \text{ ms}$ or to $> 60 \text{ ms}$ over baseline ^a . | Discontinue study drug administration and follow-up per Protocol. |

^a For elevations of the JTc interval, consultation with a cardiologist is recommended. A decision regarding dose modification or discontinuation of pemigatinib should be made in consultation with the sponsor's medical monitor.

Pemigatinib will be self-administered as a QD oral treatment on a 21-day cycle. Participants will take study drug for 2 weeks (14 days) continuously followed by a 1-week (7-day) break. The starting dose will be 13.5 mg. Based on preliminary results from the food effect cohort in Study INCB 54828-101, pemigatinib may be administered with or without food.

For dose adjustments, a maximum of 2 dose level reductions are recommended as follows: participants administered 13.5 mg can decrease to 9 mg, and if an additional dose reduction is required, participants can decrease to 4.5 mg. Dose reductions below 4.5 mg are not allowed. The frequency of administration will remain the same (QD) as well as the schedule (2 weeks on treatment followed by 1 week off treatment).

For participants who present with possible or confirmed SRD/RPED based on OCT, the guidelines in [Table 9](#) should be followed. It is recommended to discuss the findings with the sponsor's medical monitor before making changes to the participant's treatment.

Per CTCAE v5.0, retinal detachment is graded as 3 (macular sparing) and 4 (macula-off), but this refers to rhegmatogenous retinal detachment (when a hole occurs in the retina). There is no grading for SRD/RPED (no hole in the macula, just fluid accumulation). Therefore, grading should be based on the CTCAE v5.0 term of retinopathy.

6.5.2. Management of Hyperphosphatemia

Hyperphosphatemia is an expected on-target pharmacologic effect of FGFR inhibition. Hyperphosphatemia should be managed with diet modifications, phosphate binders and diuretics, or a dose reduction per the recommendations in [Table 10](#).

The use of diet modifications alone include food exchanges from high-phosphate foods to low-phosphate foods and can be implemented once serum phosphate levels are above the ULN but do not exceed 7.0 mg/dL. Diet modification should continue with the inclusion of phosphate binders once serum phosphate levels exceed 7.0 mg/dL. Examples of phosphate binders are sevelamer HCl (examples of brand names: Renegel® and Renvela®) or lanthanum HCl.

Administration of phosphate binders should be 3 times per day (eg, with each meal) to reduce absorption of phosphate. Doses and frequency of doses should be based on the participant's tolerance for the binder and the control of serum phosphate. If binders are used to manage HP during treatment, it is recommended to stop binders at the same time pemigatinib is stopped to reduce the risk of hypophosphatemia.

For grading of HP, note that CTCAE v5.0 now has a category for HP.

For Japan, the sponsor will provide the phosphate binder lanthanum carbonate hydrate for the treatment of HP when required (see [Table 10](#)).

Table 10: Recommended Approach for Hyperphosphatemia Management

| Serum Phosphate Level | Supportive Care | Guidance for Interruption/Discontinuation of Pemigatinib | Guidance for Restarting Pemigatinib |
|---------------------------|---|--|--|
| > 5.5 mg/dL and ≤ 7 mg/dL | Initiate a low-phosphate diet. | No action. | Not applicable. |
| > 7 mg/dL and ≤ 10 mg/dL | Initiate/continue a low-phosphate diet and initiate phosphate-binding therapy. Monitor serum phosphate approximately twice a week and adjust the dose of binders as needed; continue to monitor serum phosphate at least twice a week until level returns to ≤ 7 mg/dL. | If serum phosphate level continues to be > 7 mg/dL and ≤ 10 mg/dL with concomitant phosphate-binding therapy for 2 weeks, or if there is recurrence of serum phosphate level in this range, interrupt pemigatinib for up to 2 weeks. | Restart at the same dose when serum phosphate is < 7 mg/dL. If serum phosphate level recurs at > 7 mg/dL, restart pemigatinib with dose reduction. |
| > 10 mg/dL | Continue to maintain a low-phosphate diet, adjust phosphate-binding therapy, and start/continue phosphaturic agent. Continue to monitor serum phosphate approximately twice a week until level returns to ≤ 7 mg/dL. | If serum phosphate level is > 10 mg/dL for 1 week following phosphate-binding therapy and low-phosphate diet, interrupt pemigatinib. If there is recurrence of serum phosphate level in this range following 2 dose reductions, permanently discontinue pemigatinib. | Restart pemigatinib at reduced dose with phosphate binders when serum phosphate is < 7 mg/dL. |

6.5.3. Criteria for Permanent Discontinuation of Study Drug

The occurrence of unacceptable toxicity not caused by the underlying disease will require that the study drug be permanently discontinued. Unacceptable toxicity is defined as follows:

- The occurrence of an AE that is related to study drug that, in the judgment of the investigator or the sponsor's medical monitor, compromises the participant's ability to continue study-specific procedures or is considered to not be in the participant's best interest.
- An AE requiring more than 2 dose reductions.
- A persistent AE requiring a delay of therapy for more than 2 weeks (14 days) unless a greater delay has been approved by the sponsor.
- An increase in QT/QTc to > 500 milliseconds or to > 60 milliseconds over baseline. In the case of a QTc > 500 milliseconds, the participant must be hospitalized, and continuous ECG monitoring must be set up until the measure of the QTc interval decreases below 500 milliseconds and is acceptable in the opinion of the local cardiologist. For elevations of the JTc interval, consultation with a cardiologist is recommended. A decision regarding dose modification or discontinuation of pemigatinib should be made in consultation with the sponsor's medical monitor.

See Section 7 for discontinuation procedures.

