| PTH | parathyroid hormone |
| PTT | partial thromboplastin time |
| QD | once daily |
| QTcF | QT interval corrected using Fridericia's formula |
| RANO | Response Assessment in Neuro-Oncology |
| RNA | ribonucleic acid |
| RSI | Reference Safety Information |
| SAE | serious adverse event |
| SD | stable disease |
| SoA | schedule of activities |
| SOP | standard operating procedure |
| SRD/RPED | serous retinal detachment/retinal pigmented epithelium detachment |
| TACC | transforming acid coiled-coil |
| TCGA | The Cancer Genome Atlas |
| TEAE | treatment-emergent adverse event |
| TMZ | temozolomide |
| UKCA | UK Conformity Assessed |
| UKNI | UK Northern Ireland |
| ULN | upper limit of normal |
| VEGF | vascular endothelial growth factor |
| VEGFR | vascular endothelial growth factor receptor |
| V _z /F | apparent oral dose volume of distribution |
| WBC | white blood cell |
| WHO | World Health Organization |
| WHO-CNS5 | WHO Classification of Tumours of the Central Nervous System, fifth edition |
| WOCBP | woman of childbearing potential |

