8.3.5. Electrocardiograms

Single 12-lead ECGs will be obtained as outlined in the SoA (see [Table 3](#)) using an ECG machine that automatically calculates the heart rate and measures PR, QRS, QT, and QTc intervals. All 12-lead ECGs will be performed with the participant in a recumbent or semirecumbent position after 5 minutes of rest.

The 12-lead ECGs will be interpreted by the investigator at the site to be used for immediate participant management. Additional 12-lead ECGs may be performed as clinically indicated to manage participant safety. The decision to include or exclude a participant or discontinue study treatment based on an ECG flagged as "Abnormal, Clinically Significant" is the responsibility of the investigator, in consultation with the sponsor's medical monitor as appropriate. Clinically notable abnormalities that are considered clinically significant in the judgment of the investigator are to be reported as AEs. In the event that a single QTc is > 480 milliseconds at screening, the participant may enroll if the average QTc for the 3 ECGs is ≤ 480 milliseconds or with approval from the medical monitor. For participants with an intraventricular conduction delay (QRS interval > 120 milliseconds) at screening, the JTc interval may be used in place of the QTc with medical monitor approval. In addition, the JTc interval should be used for all subsequent assessments.

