8.4. Vital Signs

Values at each scheduled visit, change, and percentage change from baseline for vital signs, including systolic blood pressure, diastolic blood pressure, pulse, body temperature, respiratory rate, and weight will be summarized descriptively.

Normal ranges for vital sign values are defined in [Table 6](#). For participants exhibiting vital sign abnormalities, the abnormal values will be listed along with their cohort. Alert vital signs are defined as an absolute value outside the defined normal range and percentage change greater than 25%. Note that the definition of alert vital signs does not apply for body temperature and weight. The abnormal values for participants exhibiting alert vital sign abnormalities will be listed.

Table 6: Normal Ranges for Vital Sign Values

Parameter	High Threshold	Low Threshold
Systolic blood pressure	$\leq 155 \text{ mmHg}$	$\geq 85 \text{ mmHg}$
Diastolic blood pressure	$\leq 100 \text{ mmHg}$	$\geq 40 \text{ mmHg}$
Pulse	$\leq 100 \text{ bpm}$	$\geq 45 \text{ bpm}$
Temperature	$\leq 38^\circ\text{C}$	$\geq 35.5^\circ\text{C}$
Respiratory rate	$\leq 24 \text{ breaths/min}$	$\geq 8 \text{ breaths/min}$

8.5. **Electrocardiograms**

Twelve-lead ECGs, including the HR, PR, QT, QRS, and QTc intervals, will be obtained for each participant during the study. Values at each scheduled visit, change, and percentage change from baseline will be summarized for each ECG parameter. Baseline will be determined as the average of all nonmissing values before the first administration of pemigatinib.

Normal ranges for ECG values are defined in [Table 7](#). The ECG values will also be considered abnormal if the absolute percentage change from baseline is more than 25% (30% for QRS interval). Participants exhibiting ECG abnormalities will be listed with study visit and assigned cohort. Abnormal values for participants with alert ECG values, defined as both the absolute value and the percentage change from baseline being outside normal ranges, will be identified and listed. Outliers of QT and QTc values, defined as absolute values > 450 millisecond, > 500 millisecond, or change from baseline > 30 millisecond, will be summarized.

Table 7: Normal Ranges for Electrocardiogram Intervals

Parameter	High Threshold	Low Threshold
PR	≤ 220 ms	≥ 75 ms
HR	≤ 100 bpm	≥ 45 bpm
QT	≤ 500 ms	≥ 300 ms
QRS	≤ 120 ms	≥ 50 ms
QTc	≤ 460 ms	≥ 295 ms

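### Protocol and SAP use three different ECG measures (QTcF, an unspecified machine QTc, and QT alongside QTc) for the same QT safety question, so stopping limits and outlier counts are not tied to one quantity

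*Protocol*

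**What the plan says.** Four places address QT prolongation, and they do not use the same quantity.

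- **Protocol Section 5.2, criterion 15:** "A screening QTcF interval > 480 milliseconds is excluded". The Protocol abbreviation list expands QTcF as "QT interval corrected using Fridericia's formula". This is the only correction formula that either document names.
- **Protocol Section 8.3.5:** ECGs are recorded "using an ECG machine that automatically calculates the heart rate and measures PR, QRS, QT, and QTc intervals". No formula is given. The same section restates the 480 ms screening check without the F: "In the event that a single QTc is > 480 milliseconds at screening, the participant may enroll if the average QTc for the 3 ECGs" does not exceed that limit, or if the medical monitor approves. Where JTc replaces QTc because of a conduction delay, it should be used for all later assessments.
- **Protocol Section 6.5.3 and Table 9:** the discontinuation trigger is "An increase in QT/QTc to > 500 milliseconds or to > 60 milliseconds over baseline". Section 6.5.3 introduces it with "The occurrence of unacceptable toxicity not caused by the underlying disease will require that the study drug be permanently discontinued".
- **SAP Section 8.5:** "Outliers of QT and QTc values, defined as absolute values > 450 millisecond, > 500 millisecond, or change from baseline > 30 millisecond, will be" tabulated. The SAP abbreviation list expands QTc only as a corrected QT interval. Appendix A plans Table 3.5.3 for QT, Table 3.5.4 for QTc and Table 3.5.8 for outliers of both. No JTc table is listed.

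**The concern.** Uncorrected QT shortens as heart rate rises and lengthens as it falls, which is why a correction is applied. A limit that may be met by QT or by QTc can therefore be crossed through a change in rate while the corrected interval stays where it was. That matters in two places: a rule that leads to permanent discontinuation, and the planned outlier table.

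The second issue is comparability. This is a multicenter study that relies on the QTc calculated by the ECG machine. If machines differ in their correction, the QTc summary, the > 450 ms count and the > 30 ms count would mix different quantities. They would also not line up with the QTcF value on which participants were admitted.

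**Working it through.** The plan states no figure to reproduce here. The check holds QTcF constant, so the corrected interval does not change, and asks which limits are crossed anyway.

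**Inputs**
- Limits: > 500 ms and > 60 ms over baseline (Protocol 6.5.3, Table 9); > 450 ms, > 500 ms and change > 30 ms (SAP 8.5).
- Heart rate: 45 to 100 bpm, the normal range in SAP Table 7.
- QTcF: 400 to 480 ms. This range is assumed; its upper end is the limit in criterion 15.
- Alternative correction: Bazett. This is assumed, because the documents name no alternative.

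**Formulas**
- Fridericia: QT = QTcF × (60/HR)^(1/3).
- Bazett from the same ECG: QTcB = QTcF × (HR/60)^(1/6).

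**1. Heart rate acting through uncorrected QT, change limits.** At QTcF 420 ms:
- HR 100: QT = 420 × 0.6^(1/3) = 354.2 ms.
- HR 80: QT = 420 × 0.75^(1/3) = 381.6 ms.
- HR 60: QT = 420 ms.

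A fall from 100 to 60 bpm adds 420 − 354.2 = 65.8 ms, which is past the > 60 ms limit. A fall from 80 to 60 adds 420 − 381.6 = 38.4 ms, which is past the SAP > 30 ms limit.

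| Heart-rate fall | Added QT, QTcF 400 | QTcF 420 | QTcF 460 | QTcF 480 |
|---|---|---|---|---|
| 100 to 60 | 62.6 | 65.8 | 72.0 | 75.2 |
| 90 to 60 | 50.6 | 53.1 | 58.2 | 60.7 |
| 80 to 60 | 36.6 | 38.4 | 42.1 | 43.9 |
| 75 to 60 | 28.7 | 30.1 | 33.0 | 34.4 |

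The > 60 ms limit needs a large fall in rate. The > 30 ms limit needs only a modest one.

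**2. Heart rate acting through uncorrected QT, > 500 ms.** QT exceeds 500 ms below 46.7 bpm at QTcF 460, below 53.1 bpm at QTcF 480, and only below 35.6 bpm at QTcF 420. At QTcF 460, a fall from 60 bpm (QT 460) to 45 bpm (QT 506) crosses the limit on study. Both the heart rate and the QTc in that example stay within SAP Table 7.

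**3. Change of formula alone (QTcF at baseline, Bazett on study).**
- At QTcF 420 and 100 bpm, QTcB = 420 × (100/60)^(1/6) = 457.3 ms, or +37.3 ms. This meets both the > 450 and > 30 ms outlier limits.
- The > 30 ms limit is met above about 86 bpm (QTcF 480) to 93 bpm (QTcF 400).
- The > 450 ms limit is met above 91 bpm at QTcF 420 and above 69 bpm at QTcF 440.
- The > 500 ms limit is met above 99 bpm at QTcF 460 and above 77 bpm at QTcF 480.
- The > 60 ms limit is met only above about 122 to 139 bpm, outside the SAP normal range.

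**4. Bazett at both time points.** A rise from 60 to 100 bpm increases QTcB by 35.5 ms (QTcF 400) to 40.9 ms (QTcF 460), so the > 30 ms count is still affected.

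**5. One formula throughout.** With QTcF at baseline and on study, every scenario above shows a change of 0 ms. None exceeds 500 ms, because QTcF is at most 480 ms.

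**The case against.** The strongest reply is that the Protocol uses QTc as shorthand for QTcF. Criterion 15 says QTcF and, two sentences later, lets JTc stand in for the QTc, plainly meaning the same quantity. Section 8.3.5 repeats the 480 ms limit as QTc, and no second formula appears anywhere. This is a fair reading of intent. It also means that a clean contrast between QTcF at entry and something else afterwards would be wrong, since the unspecified QTc applies at screening too. But the reading does not fix what a machine prints, it does not reach the SAP, and it does not explain why uncorrected QT is named. Within one bullet, Section 6.5.3 uses the QT/QTc pair for discontinuation and QTc alone for hospitalization, so the pair is hard to treat as a synonym.

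A reader might infer that heart rate alone would force participants off treatment and put them in the secondary endpoint of withdrawals due to AEs. The documents do not support that. Section 6.5 calls for clinical judgment, medical-monitor consultation and attention to relatedness. Section 8.3.5 leaves discontinuation on a clinically significant ECG to the investigator, and an ECG finding becomes an AE only if judged clinically significant. Nor does a participant whose uncorrected QT already exceeds 500 ms at entry illustrate the rule, which speaks of an increase to that level.

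Other points also stand. Bazett is an assumption. The 100 to 60 bpm example starts at the edge of the normal range, while ECGs follow five minutes of rest and the SAP baseline averages all pre-dose values. QT and QTc have separate limits in SAP Table 7, so reporting both is not in itself a contradiction, and removing QT rows would be a preference. The ECG tables are marked as standard outputs whose specifications were not available for review, and the formula may be given there. Even so, the SAP text that defines the outliers should say what QTc is.

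**Conclusion.** The inconsistency is real and worth correcting. On the literal wording, uncorrected QT can meet the > 60 ms discontinuation limit or the SAP > 30 ms outlier limit through heart rate alone: 66 ms for a fall from 100 to 60 bpm and 38 ms for a fall from 80 to 60 bpm, at constant QTcF of 420 ms. If sites' machines differ in correction, which the documents neither state nor exclude, QTc summaries and the > 450 and > 30 ms counts would not be comparable across sites or with the eligibility value. A formula change alone would seldom reach the > 60 ms stopping limit. It could reach > 500 ms at ordinary rates only when QTcF is already about 460 to 480 ms.

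The documents give no heart-rate or QTc distribution, so the number of participants affected cannot be estimated. The SAP outputs concerned are descriptive safety summaries, and the primary ORR analysis is not affected.

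**What to change.** **SAP.** In Section 8.5, derive QTcF from the collected QT and heart rate for every ECG, baseline included, and use it as the QTc in Tables 3.5.4 and 3.5.8. Any uncorrected-QT rows can stay if labelled as descriptive only. For participants entered on JTc, tabulate JTc and state how it is derived, since Protocol Section 8.3.5 says it should be used for all their later assessments.

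**Protocol.** Criterion 15, Section 8.3.5, Section 6.5.3 and Table 9 must be reconciled on one named measure, with an explicit statement of whether uncorrected QT counts. Which measure and which limits govern stopping is for the sponsor to decide; no view is taken here.

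**Cost.** One programming derivation from data already collected, and minor wording changes in both documents. No additional ECGs.
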